### **Final MTD/RP2D:**

The final recommended MTD/RP2D will be based on the recommendation from the BLRM and overall clinical assessment of all available safety, PK/pharmacodynamic, and efficacy data. Lower doses of BMS-986218 may be tested if none of the planned doses are found to be tolerable as monotherapy or in combination with nivolumab. Such decisions will be made after discussion and agreement between the investigators and the BMS Medical Monitor.

### **3.2 Simulation Parameters**

Simulation study was done for monotherapy dose escalation using various hypothetical scenarios.

Ten thousand trial simulations were used for each scenario. All simulations were run using EAST 6.4.1® software BLRM module for BMS-986218 monotherapy. The number of participants to be treated in each cohort in a specific dose level and the stopping rules used to declare MTD are defined as:

- Fixed cohort size: 3
- Probability of overdosing:  $\leq 35\%$
- Target probability of toxicity: 0.33, the upper boundary of the targeted toxicity interval
- Probability of achieving the target toxicity:  $> 50\%$
- Maximum number of participants treated: 108
- Prior specification on model parameters (based on mixture prior in [Table 2](#) from [Section 1.2.3](#)):
  - $\log(\alpha_2)$ : mean -0.619 and standard deviation 1.123
  - $\log(\beta_2)$ : mean -0.304 and standard deviation 1.464
  - Correlation: -0.036
- Posterior sampling method: Metropolis Hastings
- Minimum number of participants treated at a given dose level in order to declare MTD: 6
- Maximum number of participants at a dose: 12

The provisional dose levels for BMS-986218 monotherapy are 2, 4, 7, 20, 40, 70, 100, 150 and 200 mg, with 150 mg as the reference dose.

### 3.3 Operating Characteristics of BLRM for Monotherapy

Three scenarios were investigated by selecting (1) dose-DLT relationship derived by the prior, (2) dose-DLT curve flatter than the 1 by the prior; (3) narrow safety window in order to explore how EWOC limits the risk of exposing participants from a toxic dose level, (4) all doses below the target toxicity, and (5) all doses above the target toxicity. Simulations were performed using EAST v6.4.1 BLRM with no dose skipping option.

For scenario (1), the % DLT by prior was derived using the model solving for the probability,  $p_i$  at the  $i$ th dose as follows:

$$\text{logit}(p_i) = \log(\alpha_1) + \beta_1 \log(d_{1i}/d_1^*)$$

The model can be re-written as follows:

$$p_i = \frac{\exp(\log(\alpha_1) + \beta_1 \log(d_{1i}/d_1^*))}{1 + \exp(\log(\alpha_1) + \beta_1 \log(d_{1i}/d_1^*))}$$

Using the estimates in [Section 3.2](#), the prior probability of DLTs at doses of 2, 4, 7, 20, 40, 70, 100, 150, and 200 mg is 0.02, 0.04, 0.05, 0.11, 0.17, 0.23, 0.29, 0.35, and 0.40.

The simulation results are shown in [Table 5](#) below.

**Table 5:** Simulation Results of BLRM for Monotherapy

Scenario	BMS-986218 Dose	2	4	7	20	40	70	100	150	200	MTD not Selected (%)	Fitted Median MTD	Avg Toxicity Observed (%)	Avg # Pts
By prior	% DLT	2	4	5	11	17 a	23 a	29 a	35	40	0.3	125.4	15.0	25.8
	% MTD	0.1	0.2	1	8.6	23.7	31.1	26.7	6.9	1.4				
	# Pts	3.1	3.1	3.2	3.7	4.4	5	5.8	5.1	5.1				
Flatter than the one by the prior	# DLTs	0.1	0.1	0.2	0.4	0.8	1.1	1.7	1.8	2.1	2.9	147.9	15.8	26.1
	% DLT	7	8	10	12	16 a	17 a	21 a	23 a	25 a				
	% MTD	1.1	1.3	4.5	12.1	18.1	19.1	20.4	11.3	9.3				
Narrow safety window	# Pts	3.4	3.3	3.5	3.9	4.3	4.6	5.4	5.5	7.2	0.3	156.5	13.3	28.6
	# DLTs	0.2	0.3	0.4	0.5	0.7	0.8	1.1	1.3	1.8				
	% DLT	2	4	6	8	9	16 a	18 a	32 a	80				
All low	% MTD	0.1	0.2	0.9	4	9.9	23.1	42.9	18.5	0.2	0.4	165.8	12.6	28.7
	# Pts	3.1	3.1	3.2	3.5	3.8	4.5	6.3	5.5	3.5				
	# DLTs	0.1	0.1	0.2	0.3	0.3	0.7	1.1	1.8	2.8				
All high	% DLT	2	4	6	8	14	16 a	18 a	20 a	25 a	95.4	0.5	64.2	5.1
	% MTD	0.1	0.2	0.9	5.7	14.4	19.8	26.1	19.2	13.3				
	# Pts	3.1	3.2	3.2	3.5	4.1	4.4	5.5	6	7.4				
	# DLTs	0.1	0.1	0.2	0.3	0.6	0.7	1	1.2	1.8				

a Doses with true target toxicity within the target toxicity interval (16%, 33%).

Note: % DLT, true DLT rate; % MTD, proportion of the dose selected as the MTD; # Pts, average number of patients given the dose was tried; # DLTs, average number of DLTs given the dose was tried; Fitted MTD: fitted MTD at 33% as the target toxicity rate; % toxicity observed, average proportion of DLTs.

Abbreviation: Avg = average; NA = not applicable; Pts = participants.

The average sample size was no more than 29 participants. Most scenarios have a fitted median MTD that is close to the reference dose, and the 100 mg dose was chosen as the MTD most frequently in all scenarios, except the all high and by prior scenarios. The results for the all high scenarios show how the EWOC principle limits the risk of exposing participants from a toxic dose level by not selecting an MTD in 95.4% of the simulations. The model performs well in the by prior, flat, narrow safety window and all low scenarios by correctly identifying the MTD within the target toxicity interval, (16%, 33%) at least 82%, 78%, 85%, and 78% of the time, respectively. Overall, the scenarios illustrated above demonstrate that the model performs satisfactorily in the hypothetical scenarios investigated by correctly identifying the MTD while limiting participants from receiving excessive/unacceptable toxic dose levels.

## **4 DOSE-ESCALATION PROCESS AND SIMULATION IN COMBINATION THERAPY**

### **4.1 Dose-escalation Process**

Similar to the dose escalation process for BMS-986218 monotherapy (Section 3.1), the dose-escalation recommendations for BMS-986218 and nivolumab combination therapy will be based on the inference from the Bayesian posterior and the probability (obtained from the BLRM-Copula model) that the true DLT rate for each dose lies in 1 of the following categories:

- (0%, 16%) under-dosing
- (16%, 33%) targeted toxicity
- (33%, 100%) excessive toxicity

While the Bayesian model will use DLT information of all available data from the DLT period only, clinical assessment will take into consideration the totality of available data including PK/PD from all treated participants.

Following the principle of EWOC, after gaining information of each cohort of participants, the candidate doses are the ones fulfilling the overdose criterion that there is less than 35% chance of excessive toxicity. Only the candidate doses will be considered for the next dose decision by Investigators and BMS study personnel based on a synthesis of all relevant data available from all dose levels evaluated in the ongoing study.

A combination with a lower, intermediate, or higher dose level of BMS-986218 may be considered and tested if the model recommends it. Such decisions will be made after discussion and agreement between the investigators and the BMS Medical Monitor.

#### **Stopping Rules:**

The following are the general stopping rules of BLRM during combination therapy dose escalation:

- If all of 84 DLT-evaluable participants are treated.

- If all of the current prespecified doses are considered intolerable according to the prespecified cutoff (ie, EWOC criteria), then the model will recommend stopping the current dose level, and a new intermediate dose level lower than the current lowest dose level will need to be identified.
- The maximum number of participants in a dose level will be 12. This limit is set to avoid instances in which the model could recommend adding subjects indefinitely to a specific dose level due to uncertainty in the tolerability profile.
- If, for a specific dose level, 6 participants have been treated and the chance of determining that the dose level to be the “target” dose is  $> 50\%$ , then the model will suggest to stop and declare the current dose level to be the maximum tolerated dose (MTD).

### **Model-recommended MTD:**

The MTD is the dose that satisfies the following 3 conditions:

- 1) The empirical posterior probability that the ‘DLT rate of 16% to  $< 33\%$ ’ is greater than 50%.
- 2) This probability needs to be the largest among the dose levels that satisfy the EWOC condition (ie, the probability that ‘DLT rate  $\geq 33\%$ ’ must be no greater than 35%).
- 3) Minimum number of participants (ie, 6), were treated at this dose level.

### **Final recommended MTD for combination therapy:**

The final recommended MTD for combination therapy will be based on the recommendation from the BLRM and overall clinical assessment of all available safety, PK/pharmacodynamic, and efficacy data. Lower doses of BMS-986218 may be tested if none of the planned doses are found to be tolerable as monotherapy or in combination with nivolumab. Such decisions will be made after discussion and agreement between the Investigators and the BMS Medical Monitor.

## **4.2 Simulation Parameters**

A simulation study was done for combination dose escalation using various hypothetical scenarios.

For each scenario, 1000 trial simulations were used. All simulations were run using in house-developed code via Rv3.1.2 and R2OpenBugs v3.2 software. The number of participants to be treated in each cohort in a specific dose level, the stopping rules used to identify the model recommended MTD, and other simulation parameters are defined as:

- Fixed cohort size: 3
- Probability of overdosing:  $\leq 35\%$
- Target probability of toxicity: 0.33, the upper boundary of the targeted toxicity interval
- Probability of achieving the target toxicity:  $> 50\%$
- Maximum number of participants treated: 84
- Prior specification on model parameters are as follows :
  - BMS-986218 (based on marginal prior from [Section 2.2.1](#)):

- ◆  $\log(\alpha_2)$ : mean -1.421 and standard deviation 0.637
- ◆  $\log(\beta_2)$ : mean -1.041 and standard deviation 0.832
- ◆ Correlation: 0.624
- Nivolumab (based on marginal prior in [Table 4](#) from [Section 2.2.2](#)):
  - ◆  $\log(\alpha_2)$ : mean -1.856 and standard deviation 0.404
  - ◆  $\log(\beta_2)$ : mean -2.131 and standard deviation 0.546
  - ◆ Correlation: -0.009
- Interaction parameter (from [Section 2.2.3](#))
  - ◆  $\gamma_1$  : mean 1.1 and standard deviation 0.5
- Posterior sampling method: Metropolis Hastings
- Minimum number of participants treated at a given dose level in order to declare MTD: 6
- Maximum number of participants at a dose:12

The provisional dose levels for BMS-986218 in combination with nivolumab are 7, 20, 40, 70, 100, 150, and 200 mg, with 150 mg as the reference dose.

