### **5.1.2.3 *Dose Escalation Decisions for the BMS-986218 Monotherapy Escalation (Part 1A) and the Safety Evaluation of Combination Doses of BMS-986218 with Nivolumab (Part 1B)***

The dose-escalation phase of the study will evaluate the safety and tolerability of BMS-986218, given alone or in combination with nivolumab, based on DLTs, using a BLRM (for the BMS-986218 Monotherapy Escalation [Part 1A]) and a BLRM-copula (for the Safety Evaluation of Combination Doses of BMS-986218 with Nivolumab [Part 1B]).

During the monotherapy and combination therapy dose-escalation phase, a set of approximately 3 participants will be treated at each specified dose level. Cohort tolerability assessment with subsequent participant enrollment and dose recommendation will occur when at least 2 evaluable participants within a cohort have completed an 8-week DLT period. Any toxicities that occur beyond the DLT period will be accounted for in making dose level decisions and/or dose level modifications. Additional information on DLTs can be found in [Section 7.6.1](#).

If the potential DLT occurring in the third evaluable participant regarding the specific dose level does not influence the dose recommendation by BLRM or the BLRM-copula, the next dose level may proceed without waiting for the third participant to complete the corresponding DLT observation period, after discussion and agreement between the Sponsor and Investigators. Continuous re-assessment of dose recommendation, by BLRM in the BMS-986218 Monotherapy Escalation (Part 1A) and BLRM-copula in the Safety Evaluation of Combination Doses of BMS-986218 with Nivolumab (Part 1B), will be performed for each dose level. Planned dose levels for dose escalation are provided in [Table 5.5.2-1](#).

Planned dose levels may be modified, or intermediate dose levels added, based upon the BLRM-copula analysis for combination and clinical evaluation of all available safety and PK/pharmacodynamic data. Once the tolerability (during the DLT evaluation) of a dose level has been established, additional participants may be added at that dose level to better characterize the safety, PK, and pharmacodynamic profiles.

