**Table 5.5.2-1: Dosing Schedule by Study Part**

Study Part	Tumor Types	Dose	Dose Schedule
Part 1A	all solid tumors	2, 4, 7, 20, 40, 70, 100, 150 and 200 mg	Q4W
	select solid tumors	10, 20, 35, 50, 75 and 100 mg	Q2W
Part 1B	select solid tumors	BMS-986218 starting at 20 mg	Q4W
		nivolumab 480 mg	Q4W
Part 2A	cutaneous melanoma a	ipilimumab 3 mg/kg	Q3W
		BMS-986218 at 7 mg	Q4W
		BMS-986218 at 20 mg	Q4W
		BMS-986218 at 70 mg	Q4W
Part 2B	NSCLC b	BMS-986218 at 7 mg	Q4W
		BMS-986218 at 20 mg	Q4W
		BMS-986218 at 70 mg	Q4W
Part 2C	NSCLC	BMS-986218 at doses not to exceed MTD c	Q4W
		Nivolumab d	Q4W
Part 2D	MSS CRC	BMS-986218 at doses not to exceed MTD c	Q4W
		Nivolumab d	Q4W

a Participants must have received prior immunotherapy with an anti-PD-1 or anti-PD-L1 containing regimen and must have progressive or recurrent disease after prior PD-1/PD-L1 directed therapy. Participants must not have received prior anti-CTLA-4 therapy.

b Participants must have received prior immunotherapy with an anti-PD-1 or anti-PD-L1 containing regimen. Prior anti-CTLA-4 is allowed, but for no more than 20% of participants.

c The dose(s) of BMS-986218 selected for Part 2C and Part 2D will be based on the preliminary safety, tolerability, efficacy, PK, and pharmacodynamic data. Refer to [Section 5.1.2.4](#).

d Nivolumab combination dose to be defined from Part 1B; 1 or 2 combination dose regimens will be tested.

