#### **10.1.2     *The Safety Evaluation of Combination Doses of BMS-986218 with Nivolumab (Part 1B)***

In the Safety Evaluation Combination Doses of BMS-986218 with Nivolumab (Part 1B), the starting dose of BMS-986218 will be at least 1 dose level lower than the highest monotherapy dose level of BMS-986218 demonstrating an acceptable safety profile, and will be administered in combination with nivolumab at the flat dose of 480 mg Q4W. Dose escalation and determination of MTD for the Safety Evaluation of Combination Doses of BMS-986218 with Nivolumab (Part 1B) will be guided by BLRM-copula with EWOC principle. Subsequent dose selection of the combination will be based on evaluating the recommendation from BLRM-copula and an overall assessment of all available safety and PK/pharmacodynamic data. Safety evaluation and tumor assessment will be performed Q8W (2 cycles). BLRM-copula will incorporate historical information from ipilimumab and nivolumab studies and the DLT information from the DLT period from both combination arms to estimate dose-toxicity surface, and will provide guidance for dose adjustment of either drug as needed.

While guided by the BLRM-copula, clinical assessment will take into consideration of the totality of available data including PK/pharmacodynamic from all treated participants in assigning a dose level for the next cohort of 3 participants. Six to 12 DLT-evaluable participants will be treated at

each combination dose. Additional participants may be treated at any dose combination below or at the BLRM-copula recommended dose combination for further evaluation of safety, PK, or pharmacodynamic parameters as required. A combination with a higher dose level of either drug may be considered if recommended per BLRM-copula, after consideration of all available safety, and PK/pharmacodynamic data. At no time will the dose of BMS-986218 in the Safety Evaluation of Combination Doses of BMS-986218 with Nivolumab (Part 1B) exceed the highest tolerated dose in the BMS-986218 Monotherapy Escalation (Part 1A). Up to approximately 84 DLT-evaluable participants will be enrolled in Part 1B.

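### Table 6 simulates a combination escalation starting at 7 mg, but Part 1B started at 20 mg, so its MTD-selection figures do not describe the trial's escalation, most clearly under strong synergy

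*Combined protocol and SAP*

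**What the plan says.** **Simulation.** Appendix 11, Section 4.2 sets the combination grid: "The provisional dose levels for BMS-986218 in combination with nivolumab are 7, 20, 40, 70, 100, 150, and 200 mg". The other settings include "Fixed cohort size: 3", "Minimum number of participants treated at a given dose level in order to declare MTD: 6" and "Maximum number of participants at a dose:12". No simulated starting dose is given. Section 4.3 uses five scenarios to show how the BLRM-copula performs, reports the results in Table 6, and concludes that the model behaves as expected.

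**Trial.** For Part 1B, Table 5.5.2-1 has "BMS-986218 starting at 20 mg". The Synopsis and Section 5.1.2.2 put the start one level below the 40 mg monotherapy dose, which on the planned grid is 20 mg.

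**Participants per dose.** Section 5.1.2.3, which covers both escalation parts, says "a set of approximately 3 participants will be treated at each specified dose level", with decisions possible once 2 evaluable participants have completed the DLT period. Section 10.1.2 says of Part 1B: "Six to 12 DLT-evaluable participants will be treated at" each combination dose. The same section also assigns doses to the next cohort of 3.

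**The concern.** Table 6 is the plan's only evidence on how the combination escalation behaves if the two drugs are more toxic together than expected. Its most favourable feature in that case is selection of 7 mg, the most frequently chosen MTD in three of the five scenarios (32.1%, 43.0% and 54.4%). If the trial enters the grid one level higher, those selection rates cannot be carried over. Someone relying on Table 6 would then have too favourable a picture of MTD selection under strong synergy.

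The per-dose wording raises a separate question. A site or the sponsor cannot tell whether 6 evaluable participants are needed at a combination dose before escalation, or only at some point before the MTD is declared.

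**Working it through.** **1. The scenario rates reproduce.** Inputs (Section 4.2): prior means log α = -1.421 and log β = -1.041 for BMS-986218, reference dose 150 mg; log α = -1.856 for nivolumab. With γ = 1, p_ij = 1 - (1 - p_i)(1 - q).
- q = 1/(1 + e^1.856) = 0.135; β = e^-1.041 = 0.353.
- 7 mg: logit p = -1.421 + 0.353 × ln(7/150) = -2.503, p = 0.076, p_ij = 1 - 0.924 × 0.865 = 0.20.
- 20 mg: logit p = -1.421 + 0.353 × ln(20/150) = -2.132, p = 0.106, p_ij = 1 - 0.894 × 0.865 = 0.23.

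Both match Section 4.3. The strong synergistic rates are 1.5 times these: 30% at 7 mg and 34% at 20 mg.

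**2. Table 6's # Pts are averages over all trials.** They sum to Avg # Pts:
- Additive: 4.5 + 3.7 + 3.2 + 1.6 + 0.4 = 13.4
- Synergistic: 4.8 + 3.6 + 2.5 + 0.9 + 0.2 = 12.0
- Strong synergistic: 5.2 + 3.2 + 1.8 + 0.5 + 0.1 = 10.8
- Sub-additive: 4.0 + 3.8 + 3.8 + 2.7 + 1.1 + 0.1 = 15.5
- Strong sub-additive: 3.4 + 3.5 + 4.1 + 3.8 + 2.6 + 0.4 + 0.2 = 18.0

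The footnote says the averages are conditional on the dose having been tried. With cohorts of 3, no such average could be below 3, yet Table 6 has many entries from 0.0 to 2.7. The # DLTs behave the same way: at 100 mg in the additive scenario, 0.4 × 0.28 = 0.1, as printed, where a conditional figure would be at least 3 × 0.28 = 0.84.

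**3. The simulated start is 7 mg.** The unconditional mean at 7 mg is 3.4 to 5.2 in every scenario. In the strong sub-additive scenario, 20 mg has an 11% DLT rate, so few trials starting there would step down; a simulated 20 mg start puts only 0.3-0.6 participants at 7 mg, against 3.4 in Table 6.

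**4. Re-simulation of the stated rules.** Settings: priors as in Section 4.2; cohorts of 3; P(DLT ≥ 33%) ≤ 35%; next dose maximises P(16-33%); stop when a dose has at least 6 participants and target probability above 50%, or has 12. No dose skipping is an assumption, since Appendix 11 states it only for monotherapy. Up to 8,000 trials per scenario were run.

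From 7 mg, strong synergistic scenario (8,000 trials):

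| | MTD at 7 / 20 / 40 / 70 / 100 mg (%) | No MTD (%) | Mean N |
|---|---|---|---|
| Table 6 | 54.4 / 18.3 / 10.0 / 3.2 / 0.4 | 13.7 | 10.8 |
| Re-run | 54.9 / 19.0 / 10.0 / 2.9 / 0.2 | 13.0 | 10.7 |

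**5. The same rules from 20 mg, strong synergistic scenario.** Table 6's over-toxic selection is 18.3 + 10.0 + 3.2 + 0.4 = 31.9%.

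| | MTD at a dose above 33% | No MTD | Mean toxicity |
|---|---|---|---|
| Table 6 (7 mg start) | 31.9% | 13.7% | 37.8% |
| 20 mg start, 7 mg selectable | about 40-55% | 18-21% | 35-38% |
| 20 mg start, 7 mg not selectable | about 60-66% | 34-40% | 39-44% |

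The ranges cover variants with and without 6 participants required per dose. Participants treated above 33% rise from 3.2 + 1.8 + 0.5 + 0.1 = 5.6 to about 7.5-8.3.

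**6. The other scenarios.** In the synergistic scenario, selection at 33% or above is 8.0 + 1.2 = 9.2% in Table 6 and about 7-11% from 20 mg with 7 mg selectable; no MTD goes from 7.9% to about 10-11%. The remaining three scenarios contain no dose at 33% or above.

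**7. Participants per dose.** If each dose visited had to reach 6, the mean at the starting dose would be at least 6 in any trial not stopped early. Table 6 shows 3.4 in the strong sub-additive scenario, with only 0.3% of trials ending without an MTD. The simulated rule therefore lets a trial leave a dose after 3.

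**The case against.** The strongest reply is that the appendix presents the grid for simulation purposes and the BMS-986218 prior as illustrative, and that live decisions use accumulating DLT data, a prior that is continuously updated, clinical assessment and sentinel dosing. Under the stated priors, P(DLT ≥ 33%) at 20 mg is about 17%, inside the 35% cap, so the model itself permits a 20 mg start. The strong synergistic scenario is hypothetical, its 34% at 20 mg is only just over the limit, and a higher no-MTD rate is partly the overdose control doing its job.

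Much of this stands. A reader might infer that the safety of the whole escalation is misstated. The documents do not support that: mean toxicity moves by about 3 points or less in every scenario while 7 mg remains available, and over-toxic selection worsens materially in one scenario only. A reader might also infer that cohorts of 3 conflict with the protocol. They do not, since Section 10.1.2 uses them too and the simulation has the same 6 and 12 as its MTD minimum and per-dose cap. Nor are mean totals of 10.8 to 18.0 impossible with 6 per dose: such runs gave 9.9 to 17.6.

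The size is also uncertain. It depends on skipping, on which lower doses stay available, and on near-ties in the model's preference between 7 and 20 mg; one run reached about 59% over-toxic selection. No point estimate should be used.

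What the reply does not remove is that Table 6 is offered as a demonstration of performance, was brought up to date in Amendment 07, and starts from a dose at which Part 1B did not start.

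**Conclusion.** The point holds in a limited form. Table 6 describes an escalation from 7 mg, and Part 1B started at 20 mg, so its selection, no-MTD and sample-size figures are not those of the trial. The material consequence is in the strong synergistic scenario: over-toxic MTD selection of 31.9% becomes about 40-55% or 60-66%, and no MTD of 13.7% becomes 18-21% or 34-40%, depending on whether 7 mg can still be selected. Appendix 11 allows lower doses to be considered but does not settle that question for the simulation. The direction is firm; the size rests on the no-skipping assumption and on the implementation details above.

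Two smaller points also hold. Sections 5.1.2.3 and 10.1.2 leave open whether 6 evaluable participants are needed before escalating a combination dose. The Table 6 footnote misdescribes # Pts and # DLTs.

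**What to change.** - Re-run Table 6 from the starting dose actually used. State in Section 4.2 the simulated starting dose, whether skipping is allowed, and which lower doses remain available. Restate the selection, no-MTD and sample-size figures in Section 4.3.
- Reconcile Sections 5.1.2.3 and 10.1.2 with each other and with the simulated rule in Section 4.2, so that one statement covers the evaluable participants needed before escalation and the number to be reached at each combination dose. The choice of rule is the sponsor's.
- Correct the Table 6 footnote: # Pts and # DLTs are averages over all simulated trials.

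The cost is a re-run of existing in-house code and wording changes in the appendix and two protocol sections. The restated figures for strong synergy will probably look less favourable.
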